All UC Davis ED patients who are being evaluated for ILI or URI by an ED physician during the study period will be eligible for recruitment. Once the ED research coordinator or EMRAP students identify an eligible patient, the patient will be approached by the ED Research Coordinator and asked for consent to enroll. After obtaining informed consent, patients will be randomized to one of two arms: multi-respiratory pathogen testing together with usual care or clinician directed standard of care (which may include but is not limited to no testing or targeted influenza molecular testing *Alere I Influenza A & B*) using a simple randomization scheme. In this study, the randomization scheme we are planning to use is individual randomization. To ensure that the study population includes patients treated as outpatients vs. admitted, patients will be recruited from the 'up front care' treatment area (urgent care unit for ED patients expected to be treated as outpatients), in addition to our main emergency department area.

A brief demographic and symptom questionnaire will be administered to all subjects (see attachment). If patients are assigned into the control group, they will receive clinician directed standard of care (which may include but is not limited to no testing, point-of-care influenza molecular testing *Alere I Influenza A & B*, or multi-pathogen respiratory viral panel testing at off-site laboratory performed 3-4 times weekly in scheduled batches). Conversely, patients randomized to receive the rapid FilmArray RP, will receive usual care plus have a nasopharyngeal swab collected by an ED nurse or ED physician for FilmArray RP testing. The nasopharyngeal swab will be transported to the CLIA-certified clinical laboratory located one-floor above the ED where a licensed Clinical Laboratory Scientist (CLS) will perform the FilmArray RP test in real-time. Once the test is completed, FilmArray RP results will be reported in EMR via standard procedures and be available to ED physicians for use in patient management. ED physicians are free to decide how the test results will impact their treatment decisions and whether they would like to share these results with their patients. To ensure that results are available before ED physicians make treatment decision, we will encourage the ED triage physician to order the test before patients are put into ED rooms and ensure that FilmArray RP results are reported within 2 hours of sample collection.

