In order to evaluate the impact of having rapid FilmArray RP results on clinical treatment, outcomes, and costs among ED patients, we will collect additional clinical and administrative data from EMR, laboratory, and UCDHS administrative databases. These data may include but are not limited to demographic characteristics, ICD10, CPT, and DRG diagnosis, procedure, and billing codes, charge and cost data, admission source, discharge disposition, clinical signs and symptoms of respiratory or other illness, relevant laboratory and radiology results, medications, antibiotics, antiviral and other respiratory treatments (e.g., oxygen, nebulizers and inhaled treatment) 30 days before, during, and after the ED episode of care, length of ED encounter, and data for any hospitalization, ED, or outpatient clinic visits within 30 days. These additional data collection and analysis of results will be performed for 1-5 years after completion of the active enrollment period (December 2017).

8) Data and/or Specimen Management and Confidentiality

PROTOCOL TITLE: Pilot randomized clinical trial of multi-respiratory pathogen testing versus usual care in emergency department (ED) patients with upper respiratory symptoms

Power Analysis - Based on existing literature and baseline data, we anticipate approximately 50% of patients with the diagnosis of ILI or viral URI in the control group will receive antibiotics, whereas 10% with confirmed influenza will receive antivirals. Based on the effect sizes, anticipating significant improvement in detection rates for influenza and other viral pathogens, and hypothesizing a 15 percentage point decrease in antibiotic use for patients with ILI or URI from 40 to 25% in the multi-respiratory pathogen test group, we plan to enroll approximately 304 – 325 patients over 12-18 months (June 2016 – December 2017). A sample size of at least 152 enrolled patients in each of the control and intervention arms will provide > 80% power to detect any true 15 percentage point difference between the multi-respiratory pathogen test and usual care arms.

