Data for this study will be collected from the patient questionnaire, electronically in bulk from EMR, administrative and laboratory databases, and from individual patient charts in EMR. Entry into individual patients charts (EMR) will be used primarily to clarify responses to the patient questionnaire, evaluate physician awareness of and utilization of FilmArray RP results and decision-making (e.g. to determine how the results from the rapid, multi-respiratory pathogen testing influences physicians' decision to prescribe antibiotics, to obtain respiratory radiology results), and clarify gaps in the bulk electronic data.

All data will be maintained for 5 years after completion of this project. All data will be maintained in password-protected spreadsheets/databases located on a secure UCDHS server. Patients' PHI will be removed and data assigned a unique study identifier as soon as possible after extraction and electronic matching. Access to databases with identifiable electronic data will be limited to authorized investigators, study personnel, research coordinators and analysts directly involved in the study. All signed HIPAA Authorization forms granting research personnel permission to use PHI for research will be kept in a locked cabinet in the office of the principal investigator or in a lockbox in the ED for 5 years. Any unauthorized entry into individual EMR patient records (e.g. to identify potential subjects and before the HIPAA Authorization form is signed) will be documented and reported to the UCDHS compliance office via Break the Glass on EMR.

9) Data and/or Specimen Banking

Samples – Remnant nasopharyngeal swab samples in viral transport media will be labeled with a non-PHI containing code number and kept in an access-controlled UC Davis laboratory freezer for 5 years after the active study period for potential repeat, confirmatory, or additional respiratory pathogen testing. Access to the laboratory freezer will be limited to authorized investigators and research personnel. Only authorized investigators will be allowed to request further testing on these samples.

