Data – All subjects' questionnaires and signed consent forms will be kept in locked cabinets in the office of the principal investigator or in a lockbox in the ED. Patient test results (which includes both the clinician directed standard of care and the rapid, FilmArray RP testing) will be documented in the laboratory LIS and EMR as per routine procedures. All extracted and collected data will be maintained in password-protected spreadsheets/databases located on a

PROTOCOL TITLE: Pilot randomized clinical trial of multi-respiratory pathogen testing versus usual care in emergency department (ED) patients with upper respiratory symptoms

secure UCDHS server and will be coded (e.g. stripped of PHI and assigned a unique study identifier) as soon as possible after extraction and electronic matching. Data will only be accessible to trained project personnel. Coded data will be maintained for 5 years after the study is closed.

10) Withdrawal of Subject

The investigator can decide to withdraw subjects from the study at any time due to reasons such as missing information, collection of a sample inadequate for testing or because the entire study is terminated. Subjects are also free to withdraw from the study whenever they want.

If a patient withdraws from the study, research personnel will discard the patient's remnant nasopharyngeal swab sample and no longer obtain new clinical and administrative data about the patient from EMR, laboratory and UCDHS administrative databases. However, already collected data relating to any subject who chooses to withdraw will be retained and analyzed to maintain the integrity or reliability of the research.

11) Risks to Subjects

This study poses minimal risk of harm or discomfort to subjects. For patients assigned to receive the rapid FilmArray RP test, it is possible that the collection of the nasopharyngeal swab sample may make some of them feel uncomfortable. However, there is little or no risk of injury as the swab will be administered by trained ED personnel and there should be no lasting physical or emotional harm associated with the procedure. This procedure also has no risks to an embryo or fetus should the patient be or become pregnant.

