There will be no risk to patients placed in the usual care control group since they will receive the clinician directed standard of care (which may include but is not limited to no testing, point-of-care influenza molecular testing *Alere I Influenza A & B*, or multi-pathogen respiratory viral panel testing at off-site laboratory performed 3-4 times weekly in scheduled batches); patients will receive similar treatment should they decide not to be enrolled in this study.

12) Potential Benefits to Subjects

Patients who are assigned to receive the rapid FilmArray RP test may or may not benefit directly from participating in the study. There are no guidelines on how physicians should utilize the results; instead, physicians are free to decide how the results will impact their decision-making. Depending on how physicians use the results, a possible benefit these patients may have is not receiving unnecessary antibiotics for viral infection.

Patients placed in the usual care control group will receive no direct benefit from this study. However, we expect general benefits to the public as our study results may have the impact to change the clinical paradigm and testing/treatment strategy when diagnosing IRI or URI in ED patients.

13) Community-Based Participatory Research

PROTOCOL TITLE: Pilot randomized clinical trial of multi-respiratory pathogen testing versus usual care in emergency department (ED) patients with upper respiratory symptoms

This study is limited to UCD Emergency Department patients; there will be no community participation.

14) Sharing of Results with Subjects

The rapid FilmArray RP test results will be released by CLS and reported to physicians through EMR. Physicians may decide if they would like to share these results with subjects.

Results from clinician directed standard of care test results will also be released to physicians through EMR as per standard hospital protocol.

15) Prior Approvals

This clinical trial is sponsored by BioFire Diagnostics and thus the contract between BioFire and UC Davis Health Systems must be approved before this study is conducted.

16) Provisions to Protect the Privacy Interests of Subjects

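### Section 10 lets the investigator withdraw randomised patients for an inadequate sample, a ground that falls almost only on the FilmArray arm, and does not secure their outcomes

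*Combined protocol and SAP*

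**What the plan says.** All references are to the combined protocol and SAP.

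- **Grounds for withdrawal (section 10, Withdrawal of Subject).** The investigator may withdraw a subject at any time "due to reasons such as missing information, collection of a sample inadequate for testing", or because the whole study is terminated.
- **Order of events (section 7, Procedures Involved).** "After obtaining informed consent, patients will be randomized to one of two arms". Patients assigned to FilmArray "will receive usual care plus have a nasopharyngeal swab collected by an ED nurse or ED physician for FilmArray RP testing". No study swab is described for controls. They receive clinician-directed care, which may involve no test, a point-of-care influenza test, or "multi-pathogen respiratory viral panel testing at off-site laboratory performed 3-4 times weekly in scheduled batches" (sections 7 and 11).
- **After withdrawal (section 10).** If a patient withdraws, personnel will "no longer obtain new clinical and administrative data about the patient from EMR" and the other databases. The next sentence says that "already collected data relating to any subject who chooses to withdraw will be retained and analyzed".
- **Outcome window (section 7).** Planned data include treatments during and after the ED episode and "data for any hospitalization, ED, or outpatient clinic visits within 30 days".
- **Data source (section 8).** Most data come by bulk electronic extraction. Individual chart review is planned, among other uses, to "clarify gaps in the bulk electronic data".

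The document has no intention-to-treat statement, no definition of an analysis population and no dropout allowance.

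**The concern.** The trial compares a testing strategy with usual care. A swab that cannot be tested is one of the ways the strategy performs in practice, so those patients belong in the FilmArray arm's result. Section 10 allows them to be removed after randomisation, at the investigator's discretion, for an event that the study procedures create in one arm only. A control could meet the same ground only through a sample that a clinician chose to order.

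If the discretion is used and the outcomes are lost, the FilmArray arm becomes a selected group while the control arm largely does not. The antibiotic comparison, on which the sample size rests, and the 30-day comparisons would then no longer be fully randomised.

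The missing-information ground is different. It can arise in either arm, so it is not one-sided, but it too permits loss after randomisation.

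**Working it through.** **1. Is the ground one-sided?** Consent comes first, then randomisation, then a study swab in the FilmArray arm only. Section 4 makes agreement to a swab a condition of eligibility for everyone, but no section describes taking one from controls. The ground is therefore almost entirely, though not strictly, confined to FilmArray.

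**2. What happens to the data?**

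| Sentence in section 10 | Whom it names | Investigator withdrawals covered? |
|---|---|---|
| New data collection stops | A patient who withdraws | Not stated |
| Collected data kept and analysed | A subject who chooses to withdraw | Not stated |

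- If both sentences are confined to patient-initiated withdrawal, nothing governs the patients the investigator withdraws.
- If both are read broadly, data in hand are kept, but anything not yet extracted is lost, including later treatment and 30-day visits. Because extraction is in bulk, what would count as already collected on the day of withdrawal is undefined.
- Neither reading secures complete outcomes for these patients.

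**3. The plan's own figure.** Section 8 gives 40% versus 25% antibiotic use and at least 152 per arm for more than 80% power. (It also mentions a 50% control rate, which is a separate matter; 40% is used here because the 15-point difference is built on it.) Two-sided alpha of 0.05 is assumed, since none is stated. With a pooled z test:

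n = [1.960·√(2·0.325·0.675) + 0.842·√(0.40·0.60 + 0.25·0.75)]² / 0.15² = 151.9, so 152 per arm, with power 80.0%. The figure reproduces.

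**4. Effect of losing FilmArray patients.** Let p be the arm's true rate, w the share lost and p_w the antibiotic rate in those lost. The observed rate is (p − w·p_w)/(1 − w). The documents give neither w nor p_w. Taking w as 5% or 10% (about 8 or 15 of 152), and complete loss of outcomes as the worst case:

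*Planned effect: p = 25%, lost patients prescribed at the usual-care 40%*
- w = 5%: (0.25 − 0.05·0.40)/0.95 = 24.2%; difference 15.8 points instead of 15.0.
- w = 10%: (0.25 − 0.10·0.40)/0.90 = 23.3%; difference 16.7 points.

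*No effect: 40% in both arms, type I error from a normal approximation with 152 controls*

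| w | p_w | Observed FilmArray rate | Shift (points) | Two-sided type I error |
|---|---|---|---|---|
| 2% | 60% | 39.6% | 0.4 | 5.1% |
| 5% | 60% | 38.9% | 1.1 | 5.4% |
| 5% | 20% | 41.1% | 1.1, opposite direction | 5.4% |
| 10% | 60% | 37.8% | 2.2 | 6.7% |
| 10% | 20% | 42.2% | 2.2, opposite direction | 6.7% |
| 10% | 80% | 35.6% | 4.4 | 12.2% |
| any | 40% | 40.0% | 0 | 5.0% |

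The standard error of the difference is about 5.7 points: for w = 5% and p_w = 60%, √(0.40·0.60/152 + 0.389·0.611/144.4) = 0.057.

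**5. Power.** With 152 per arm, losing 5% or 10% of FilmArray lowers power from 80.0% to about 79% or 78%. At 162.5 per arm (325 in total) it goes from 82.6% to 81.6% or 80.4%. Power is not the issue.

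**The case against.** The strongest reply is that section 10 plans no exclusion. The investigator may withdraw such patients but need not. No sentence drops them from the analysis, and the only sentence on analysing withdrawn subjects' data points towards keeping it. Complete loss needs the stop-collection sentence to reach investigator withdrawals while the retention sentence does not, an asymmetry the wording does not support.

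The size is also built on assumptions. With 2% lost and a 20-point gap, or 5% lost and a 10-point gap, type I error stays near 5.1%. Simulation with binomial counts gives about 5.2% with no loss at all, so the 5.4% case adds little. No mechanism is offered for patients with poor swabs to differ by 20 points in prescribing when testing has no effect. This is also a pilot, and the consent text, which might address data use after withdrawal, is not in the public copy.

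Much of this stands as a limit on size. Complete loss is the worst case, the rates are assumed, and the likely bias is small. It does not remove the point. A written rule permits removal after assignment on a ground peculiar to one arm, and even the favourable reading loses data not yet extracted. Discretion without stated criteria, used once the arm is known, is itself the weakness. Pilot status helps little, because section 3 intends the results to guide larger trials and section 8 powers a two-arm comparison.

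One further objection is fair: one-sidedness does not justify deleting the missing-information ground. That deletion rests on the separate reason that it also allows avoidable loss after randomisation.

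**Conclusion.** The concern holds. Section 10 permits removal of randomised patients for an inadequate sample almost only in the FilmArray arm, and the document neither guarantees their outcomes nor says that everyone is analysed as assigned. How far data would be lost is ambiguous, because neither follow-on sentence names investigator withdrawals.

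Under assumed losses of 5% to 10% of the FilmArray arm with no outcomes retained, the planned difference is overstated by 0.8 to 1.7 points if the lost patients are prescribed at 40%. Under no effect, a 20-point prescribing gap in either direction moves the FilmArray rate by 1.1 to 2.2 points. A larger gap does more, and there is no bias if the lost patients resemble the arm average. True size and direction are unknown. This is a modest bias that should be removed because doing so is cheap; it does not threaten the trial as a whole.

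**What to change.** Amend section 10 as follows.

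1. Remove inadequate sample and missing information as grounds for withdrawal by the investigator.
2. Record patients with an inadequate sample as having no FilmArray result available, and keep them in their assigned arm.
3. Continue the planned record and administrative extraction through 30 days unless the patient withdraws permission, and use the chart review in section 8 to fill gaps. Check this against the consent and authorisation wording.
4. Extend the retention sentence to any remaining withdrawals by the investigator.
5. State that all randomised patients are analysed as assigned, and report the number of inadequate samples by arm.

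The cost is a short amendment. The extraction and chart review are already planned, and there is no added patient burden. The one statistical price is that untested FilmArray patients slightly dilute the observed effect compared with an analysis of tested patients only. That dilution is part of the effect of offering the test.
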